3.3 TREATMENT OF SUBJECTS

All subjects will receive 12 weeks of treatment with SOF/VEL/VOX.

SOF/VEL/VOX FDC will be administered orally once a day. The 1st dose will be taken on Day 0.

3.4 DOSE MODIFICATIONS / TOXICITIES

Maximal suppression of HCV replication is most likely accomplished by sustained delivery of antiviral agents at their current recommended doses. Dose reduction would compromise this goal and predispose to the emergence of drug-resistant viral variants. Hence, no dose reduction will be allowed for SOF/VEL/VOX.

3.4.1 Dose Modification for SOF/VEL/VOX

Dose modifications will not be permitted. If a subject forgets to take the medication at the correct time, it may be taken later in the day; however, no more than a single dose should be taken on any calendar day. The subject should resume the standing dosing schedule on the next day. Any treatment interruption or discontinuation will be recorded including the reason for the interruption or discontinuation.

3.4.2 Treatment Failure / Drug Discontinuation

See also Criteria for premature withdrawal of subjects (2.20.2). Subjects will be considered treatment failures and will discontinue SOF/VEL/VOX FDC if they meet any of the following criteria while taking study drugs:

- HCV RNA greater than LLOQ after 2 prior consecutive HCV RNA values less than the LLOQ
- Greater than a 1 log₁₀ increase in HCV RNA from nadir
- Less than a 2 log₁₀ decline in HCV RNA after 4 weeks of treatment (unless >2 log drop would be below LLOQ)
- HCV RNA \geq LLOQ after 8 weeks of treatment

If any of these should occur in a patient who is currently on study drugs, the subject should return within one week for a confirmatory test. If the confirmatory test also meets the same criteria, the subject will be considered a treatment failure and should be discontinued from therapy. The anticipated clinical impact of discontinuation should be discussed in advance with the Medical Monitor (MM) if possible, particularly if discontinuation is thought to pose a risk to the overall clinical wellbeing of the subject. Those who are discontinued will continue to follow the general study schedule of assessments unless unwilling to do so, in which case they may be seen at least every 12 weeks for safety and research labs until the end of the study. Subjects will be followed closely for resolution of active laboratory abnormalities or adverse events which are considered related to the study agents prior to starting the revised schedule.

Subjects who meet any of the following laboratory criteria must stop all study medication(s):

- Elevation of ALT >5x OR AST >5x Day 0, confirmed by immediate repeat testing
- Abnormal elevation of ALT >3 x Day 0 *and* total bilirubin >2 x ULN, confirmed by immediate repeat testing
- Elevation of ALT >15 x ULN confirmed by immediate repeat testing
- Any Grade 3 or greater rash associated with constitutional symptoms
- Any Grade 4 event assessed as related to treatment with SOF/VEL/VOX FDC
- Pregnancy

3.4.3 Treatment Failure Criteria After Stopping SOF/VEL/VOX

• Have detectable HCV RNA during the post-treatment period (after having achieved HCV RNA <LLOQ at end of treatment). If virus is detected after subject achieves SVR12, will confirm with repeat viral testing, and then evaluate for reinfection versus relapse with viral subtyping and sequencing.

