4.1.1 Primary Endpoint

The primary efficacy endpoint is SVR₁₂ (HCV RNA <LLOQ 12 weeks after cessation of therapy).

The primary statistical hypothesis for efficacy is that SVR_{12} rate is higher than the conservative estimate of $70\%^{20}$.

- $H_0: SVR12 = 70\%$
- $H_a: SVR12 \neq 70\%$

The primary analysis will be intention-to-treat, including all enrolled subjects into the study and received at least one dose of study drug, performed after all enrolled subjects have been followed through 12 weeks post-treatment or discontinued from study.

4.1.2 Secondary Endpoints

Secondary efficacy endpoints include: HCV RNA < LLOQ at 4 and 24 weeks after discontinuation of therapy (SVR₄ and SVR₂₄); viral breakthrough; and relapse.

Descriptive summaries and listings will be provided for additional efficacy evaluations of the proportion of subjects who experience virologic failure and other endpoints of interest including ALT normalization, serum HCV RNA actual values, and change from baseline.

Exploratory analyses may be performed to assess the relationship between demographic, baseline characteristics, (including baseline viral load, genotype, age, sex, race, ethnicity, presence/absence of cirrhosis, baseline ALT level, prior treatment experience, response to previous treatment [if applicable], and BMI) and antiviral activity (HCV RNA reduction, proportion of subjects with HCV RNA <LLOQ at various time points during and following discontinuation of all therapy). Predictive factors of antiviral activities may be examined using regression type of analysis. Changes in HCV specific CD8 responses in patients with cirrhosis and not with cirrhosis. Changes in HCV specific immune responses in patients treated with single (NS5B) DAA versus dual (NS5B + NS5A) versus triple combination DAA (NS5B + NS5A + NS3) using samples from SPARE and this study

4.1.3 Safety Endpoints

The primary safety endpoint is any AE leading to permanent discontinuation of study drug(s).

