4.2 DATA HANDLING CONVENTIONS

Missing data can have an impact upon the interpretation of the trial data. Other than the endpoints discussed below, values for missing data will not be imputed.

For the analysis of post-baseline categorical efficacy endpoints, if a data point is missing and is preceded and followed in time by values that are deemed successes, then the missing data point will be termed a success; otherwise the data point will be termed a failure.

Any subject with missing data due to premature discontinuation of the study medication will be considered a failure at the time points on, or following, the date of discontinuation. If no HCV RNA values are obtained after the last dose of study medication, the subject will be considered a treatment failure for the SVR endpoints.

Where appropriate, safety data for subjects that did not complete the study will be included in summary statistics. For example,

- If a subject received study medication, the subject will be included in a summary of adverse events according to the treatment received; otherwise, if the subject is not dosed then they will be excluded from the summary.
- If safety laboratory results for a subject are missing for any reason at a time point, the subject will be excluded from the calculation of summary statistics for that time point. If the subject is missing a pre-dose value, then the subject will be excluded from the calculation of summary statistics for the pre-dose value and the change from pre-dose values.

Values for missing vital signs data will not be imputed; however, a missing Day 0 result will be replaced with a screening result, if available.

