8.5 SPECIFIC STUDY HALTING CRITERIA

8.5.1 Criteria to Pause Enrollment

- **Study will be paused** and the MM will be asked to review the data if 1: 3 participants experience virologic or therapeutic treatment failure while receiving treatment (see Dose Modification 3.4.1 and Treatment Failure Sections3.4.2)
- Dosing will be discontinued if 3 or more participants develop a similar related Grade 4 toxicity (excluding neutropenia, anemia, anorexia, weight loss and ALT and AST elevations). Further dosing will require review and approval after discussion with the MM. Grade 4 toxicities that result from patient non-compliance with medications for unrelated events will not be considered toward discontinuation.
- Enrollment will also be halted if the PI decides to stop or cancel the study or if the IRB or the FDA requests that the study be stopped.

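### Does leaving relapse undefined, with detectable RNA in the post-treatment rule and <LLOQ in the SVR endpoints, put any result in doubt?

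*Combined protocol and SAP*

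**What the plan says.** - **SVR.** Section 4.1.1 defines the primary efficacy endpoint as "HCV RNA <LLOQ 12 weeks after cessation of therapy". Section 4.1.2 and the abbreviation list use the same limit for SVR4 and SVR24.
- **Relapse and virologic failure.** Section 4.1.2 ends its list of secondary efficacy endpoints with "viral breakthrough; and relapse". It then plans descriptive summaries of "the proportion of subjects who experience virologic failure and other endpoints of interest". It defines neither term and cites no other section for them.
- **Failure after treatment.** Section 3.4.3 sets the criterion "Have detectable HCV RNA during the post-treatment period (after having achieved HCV RNA <LLOQ at end of treatment". It continues: "If virus is detected after subject achieves SVR12, will confirm with repeat viral testing, and then evaluate for reinfection versus relapse", using viral subtyping and sequencing.
- **Failure on treatment.** Section 3.4.2 works with LLOQ or log changes, for example "HCV RNA greater than LLOQ after 2 prior consecutive HCV RNA values less than the LLOQ", and applies only while study drug is being taken. The pause rule in 8.5.1 is likewise limited to on-treatment failure: "3 participants experience virologic or therapeutic treatment failure while receiving treatment".
- **Missing data.** Under section 4.2, if there is no HCV RNA value after the last dose, "the subject will be considered a treatment failure for the SVR endpoints".
- **Other wording.** Section 2.19 sorts subjects by detectable or undetectable RNA. The precision statement in 4.1 refers to the limit of detection.

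**The concern.** Many quantitative assays separate three states: not detected, detected but below LLOQ, and quantifiable. Section 3.4.3 uses *detectable* and <LLOQ in one sentence for two time points, which invites a reader to treat them as two limits. If they are, a subject who is <LLOQ at end of treatment and detected but <LLOQ at post-treatment week 12 meets SVR12 under 4.1.1 and fails under 3.4.3.

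Two analysts could then report different relapse counts from one dataset, and the relapse table might not agree with the SVR table. The set of virologic failures chosen for resistance monitoring in 5.1 could shift too, because 5.1 does not say where failure is defined. Few failures are expected, so even one or two reclassified subjects would show.

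**Working it through.** **1. Does the primary analysis depend on the ambiguity?** Inputs from 4.1 and 4.1.1: n = 120, null rate 70%, two-sided exact one-sample binomial test at 0.05. With at most 0.025 in each tail, the test rejects at 95 or more, or 73 or fewer, successes (actual tails 0.0159 and 0.0200). Power is 0.641 at a true 80% and 0.968 at a true 85%, which reproduces Table 4-1. A success in this test is RNA <LLOQ at 12 weeks, and neither relapse nor 3.4.3 enters. The effect on the primary result is 0.

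**2. Could 3.4.3 reach the primary result by another route?** Only if a failure under 3.4.3 cancelled an SVR12 success, which no section says. As a bound, let q be the assumed share of SVR12 achievers with a detected-but-<LLOQ result. The success rate would become p(1 − q). At p = 0.85:

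| q (assumed) | rate | power |
|---|---|---|
| 1% | 0.85 × 0.99 = 0.8415 | 0.943 |
| 2% | 0.85 × 0.98 = 0.8330 | 0.906 |
| 5% | 0.85 × 0.95 = 0.8075 | 0.716 |

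At p = 0.95, power stays above 0.999 for all three. These figures describe a rule the plan does not contain.

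**3. Size for the relapse percentage.** One subject is 1/120 = 0.83 points. If the denominator is subjects <LLOQ at end of treatment, and 95% reach that (assumption), it is 0.95 × 120 = 114, and one subject is 1/114 = 0.88 points. For an assumed 0 to 3 subjects, the shift is 0 to 3/120 = 2.5 points, or 0 to 3/114 = 2.6 points. The documents give no LLOQ, no detection limit and no frequency of intermediate results, so the range 0 to 3 is illustrative.

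**4. Are two limits really intended?** Section 4.1 describes the proportion being estimated as suppression below the limit of detection, in the paragraph that sets the expected SVR and computes its precision as 1.96 × √(0.8 × 0.2/120) = 0.07. That is the quantity 4.1.1 defines by LLOQ. Section 2.19 sends subjects with undetectable RNA at end of treatment to the SVR4, SVR12 and SVR24 visits for as long as they stay undetectable. It therefore describes end-of-treatment status by detectability where 3.4.3 uses <LLOQ. Both passages read more naturally as loose wording for one state than as a second threshold.

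**5. Can the endpoint be computed?** Section 5.1 schedules HCV RNA at end of therapy and at post-treatment weeks 4, 12 and 24. Whichever reading is taken, the count comes from data already collected. With relapse taken as RNA at or above LLOQ after <LLOQ at end of treatment, nobody can be an SVR success and a relapse at the same visit.

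**6. Does it reach trial conduct?** The pause rule in 8.5.1 counts failures during treatment, which 3.4.2 sets by LLOQ or log change. The word in 3.4.3 does not enter it.

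**The case for a change.** The strongest case is that a named endpoint should be defined before the data are seen, and that a definition costs only a sentence. Failures will be few. Section 1.6.4 cites efficacy of 95–97%, which on 120 subjects leaves 0.05 × 120 = 6 to 0.03 × 120 = 3.6 non-responders. Even if all six were relapses, one extra would raise the count by 1/6 = 17% and three would raise it by 3/6 = 50%. The resistance objective looks especially at relapse or breakthrough, so membership of that small group matters. The repeat test in 3.4.3 does not settle the threshold, since it is stated only for virus found after SVR12.

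The textual part of this stands: 4.1.2 gives no threshold or denominator, and no passage says the two terms are equivalent. The consequence does not stand as a demonstrated error. It needs intermediate assay results and the use of 3.4.3 as the analysis definition. Section 3.4.3 sits under dose modification and toxicities, and 4.1.2 does not refer to it. A bare threshold added to 4.1.2 would not be a clear gain either. Without the reinfection work-up that 3.4.3 already requires after SVR12, a reinfection found at week 24 would be counted as a relapse.

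**Conclusion.** No change to the plan is called for. The wording is uneven and the relapse definition is left unwritten, but this is missing detail that an analyst would fill with the limit used for every SVR endpoint, alongside the relapse-versus-reinfection evaluation in 3.4.3. The effect on the primary SVR12 analysis is zero, and no hypothesis test is attached to relapse or virologic failure. The possible effect is 0.83 to 0.88 points per affected subject in a descriptive percentage, with the number of such subjects unknown and possibly zero.

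This rests on two readings: that SVR12 is scored by 4.1.1 as written, with no override from 3.4.3, and that the detectability wording in 2.19, 3.4.3 and 4.1 is loose usage. If the second is wrong and the assay does report detected-but-<LLOQ values, the disagreement stays within secondary and descriptive tables and the choice of samples for resistance work. It could be resolved there from the recorded RNA results.

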3.4.4 Viral Co-infection Rebound Schema

For HIV suppressed subjects taking ARVs, at least two consecutive and uptrending postbaseline visit plasma HIV RNA levels \geq 400 copies/mL (at least two weeks apart) will be considered HIV virologic rebound.

Following an initial HIV RNA result of \geq 400 copies/mL, subjects will continue to take their current ARV regimen and be asked to return to the clinic after 2 weeks for a scheduled or unscheduled blood draw for confirmation of HIV virologic rebound. If HIV virologic rebound is confirmed at the scheduled or unscheduled visit, the blood samples from this visit will be used for HIV genotype/phenotype testing. If no resistance to the subject's current ARV regimen is detected, the subject may continue on current ARV regimen.

HCV study drug should be continued unless safety events or HCV response based stopping criteria warrant the discontinuation of the study drug, as outlined in Section 3.4 of the protocol.

For those with chronic HBV infection taking chronic suppressive therapy, if HBV flare does occur, monitoring and treatment plan will be discussed with medical monitor on an individual basis.

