2.4.1 Inclusion Criteria

A subject must meet all of the following criteria:

- 1. At least 18 years of age or older at screening.
- 2. Available for clinical follow-up through Week 44 after enrollment.

- 3. Recurrent HCV GT-1 infection as documented by ≥ 1 measurement of serum HCV RNA ≥ 1,000 IUM/mL during screening and documented history of receiving prior HCV treatment.
- 4. Exposure to combination DAA therapy, including, but not limited to, the following regimens:
 - a. $LDV/SOF \pm RBV$
 - b. Viekira Pak \pm RBV
 - c. $EBR/GZR \pm RBV$
- 5. Ability to communicate effectively with the study investigator and other key personnel.
- 6. Opioid-dependent individuals must be participating in a supervised treatment program or considered stable at the discretion of the investigator.
- 7. Subjects must have a primary care doctor for their medical management.
- 8. Able and willing to complete the informed consent process.
- 9. Willing to donate blood for sample storage to be used for future research.
- 10. Female study participants with childbearing potential (as defined below) and all male study participants must be willing to practice either:
- Complete abstinence from sexual intercourse with a member of the opposite sex **OR**
- At least one form of effective contraception from the list below, in addition to correct use of either a male or female condom with spermicide, throughout dosing and for a defined period following the last dose (30 days for women, 14 days for men) of study medication.:
 - i. Intrauterine device with a failure rate of <1% per year
 - ii. Tubal sterilization
 - iii. Bilateral tubal occlusion
 - iv. Vasectomy in a male partner
 - v. Female barrier method (diaphragm or cervical cap) with spermicide
 - vi. Hormonal methods
 - 1. Oral contraceptives
 - 2. Injectable progesterone
 - 3. Implants of levonorgestrel or etonorgestrel
 - 4. Transdermal contraceptive patch
 - 5. Contraceptive vaginal ring
- 11. Hepatitis B coinfected participants, must have evidence of chronic infection and controlled on treatment.
- 12. HIV coinfected participants only must have HIV status of one of the following:
 - a. HIV untreated for ≥ 8 weeks prior to Screening

- i. CD4 T-cell count >500 cells/mm³ at Screening
- ii. No intention of initiating ARV therapy for the duration of trial

OR

- b. HIV suppressed on a stable, protocol-approved, ARV regimen for \geq 4 weeks prior to Screening

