2.8 CLINICAL PROCEDURES AND SCHEDULE OF EVALUATIONS

This section describes the clinical procedures for evaluating study participants and follow-up after administration of study drug.

Study visits, including screening, will occur at the UMB Institute of Human Virology clinic or one of the clinics mentioned in the study roster based upon scheduling availability to accommodate each treatment group. Participants in the pharmacokinetic or viral kinetic substudy will be seen at the University of Maryland Medical Center.

UMB Study Team Roles at Washington, DC community clinics: Members of the study team have been actively involved in patient care at the community clinics (Unity's Parkside and Walker-Jones). Unity will sign a UMB Reliance Agreement prior to initiating any study activities. The site AI and collaborating investigator may see subjects at non-study visits and will communicate findings to UMB study team. The UMB research coordinators will also oversee research operations in the clinics and at the UMB IHV clinic. The UMB study staff will see participants for all scheduled and unscheduled visits and study withdrawal.

If subjects are seen in the Community: All phlebotomy will be done by a phlebotomist working in the clinic or clinic staff. A specimen bag and specimen tubes will be prepared by UMB staff and will be labeled with the participant's first three initials of last and first name and study number. All laboratory studies will be performed by UMB and will be reviewed by UMB staff on a weekly basis. Copies of results will be sent to the primary care provider and scanned into the electronic medical record at the participating clinic.

Clinic staff will not participate in study-related visits unsupervised by UMB study staff. Participants will be given a calendar of scheduled study visits and will be informed that any clinic visits outside of scheduled study visits may be either unscheduled visits or non-study visits. All visits related to the treatment of HCV will be considered study related. Any other medical problems will be addressed by the participant's primary provider. Participants will receive this information when given the visit calendar.

The primary responsibility of the site AI and the community clinics is to provide timely and effective communication regarding any potential adverse events if a subject/patient is seen for care outside of the normal study visit.

2.8.1 Screening

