2.20.1 Follow-up of Abnormal Laboratory Test Values

In the event of unexplained abnormal laboratory test values, the tests should be repeated immediately and followed up until they have returned to the normal range and/or an adequate explanation of the abnormality is found. If a clear explanation is established it should be recorded.

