This will be performed in HIV coinfected individuals at the following study points: screening, day 0, weeks 4, 8, 12 and post-treatment week 12.

CD4 Test

This will be performed in HIV coinfected individuals at the following study points: screening, week 12 and post-treatment week 12.

HBV DNA Test

This will be performed in chronically HBV-infected individuals at the following study points: day 0, on-treatment weeks 4, 8, and 12 and post-treatment weeks 4 and 12.

VK/PK Sub Study

Subjects will have blood drawn at time points 0, 1, 2, 4, 8, 24 and 72 hours after administration of drug to assess drug levels and HCV viral load levels.

Research tests

HCV Virologic Studies

Full length HCV genome pyro sequencing may be performed using the protocol as described and compared for variability of sequences²⁷.

DNA Methylation Studies

Promoter methylation status for candidate genes or at a whole genome level using methylation–specific PCR may be performed on tissue samples²⁸.

rs12979860 (IL28B) Genetic Variant

IL28B genetic variants have been shown to predict HCV treatment induced clearance²⁹. The IL28B assay is a real-time PCR assay that utilizes 5-prime nuclease activity of a thermostable polymerase and unique primers and SNP-specific probes to determine the genotype. Test results will not be used as inclusion or exclusion criteria.

Immune Responses to HCV

Both humoral and cellular immunity against HCV will be estimated before and during treatment to assess the effect of HCV treatment on host immune response against HCV. We may also perform multiplex PCR assays to detect ISGs before and during treatment.

HCV Genotypic and Phenotypic Resistance Monitoring

Serum samples for genotypic and phenotypic monitoring will be collected. Resistance monitoring will be completed in all subjects who received study drug and where virologic failures as defined.

Subjects who are determined by sequencing and phenotypic analysis to have had mutations leading to SOF resistance will be requested to return at 12 week intervals for up to 48 weeks after the last dose of study drug to determine the time for the resistant virus to return to background levels.

Immunophenotyping for T cells

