8.4 SAFETY MONITORING PLAN

Ongoing Safety Monitoring by the Study Team: Cumulative safety data will be monitored by the study team (PI and SC). Upon recognition of any safety concerns, a teleconference may be held with the MM to discuss the concern. The PI will notify the MM and Gilead Clinical Safety Office (CSO) when enrollment begins and will provide verification of safety assessments to the MM and CSO. The ISM will review the viral kinetic, pharmacokinetic and resistance data to advise regarding continued study enrollment. The study team in collaboration with the study sponsor will then make a determination about whether the study enrollment needs to shut down.

Patient safety will be monitored by the PI and study team. Patient clinical data, safety data and virologic response will be monitored at weekly (or less frequently, as indicated by protocol activity) meetings by the study team and a summary report of these reviews will be retained as part of the study records. A complete evaluation of safety and efficacy data will be obtained when the first 20 patients complete 12 weeks of therapy. Thereafter, safety and data analysis will be performed every 12 weeks through completion of the study.

Additionally, the PI will be responsible for submitting the IRB Continuing Review package and will provide the necessary safety data for the FDA IND Annual Report.

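### The HIV rebound rule in section 3.4.4 requires rising values, so a repeat still at or above 400 copies/mL but not higher does not trigger the mandated resistance test at the confirmation draw

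*Combined protocol and SAP*

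**What the plan says.** Section 3.4.4 applies to HIV-coinfected subjects who are suppressed on antiretrovirals. Rebound means "at least two consecutive and uptrending postbaseline visit plasma HIV RNA levels" of at least 400 copies/mL, taken at least two weeks apart. After a first value at or above 400, the subject stays on the current regimen and returns after two weeks for a confirmation draw. If rebound is confirmed there, "the blood samples from this visit will be used for HIV genotype/phenotype testing". If no resistance to the current regimen is found, the subject may stay on it. The section does not define *uptrending*. It gives no separate instruction for a repeat that is still at or above 400 but level or lower.

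Section 5.1 schedules HIV RNA in coinfected subjects at "screening, day 0, weeks 4, 8, 12 and post-treatment week 12". Section 2.18 places post-treatment week 12 at study week 24. The resistance monitoring described in section 5.1 stands under the HCV heading and is not an HIV rule.

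For comparison, section 3.4.2 confirms HCV failure on treatment by a repeat test within one week: "If the confirmatory test also meets the same criteria, the subject will be considered a treatment failure".

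**The concern.** The definition combines a level (400 copies/mL or more, twice) with a direction (rising), and the only mandated HIV resistance test in the protocol depends on both. A subject with high, persistent viremia whose repeat happens to be slightly lower falls outside the rule. A subject just above the threshold whose repeat is slightly higher falls inside it. Measurement noise alone can decide between the two.

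What is at stake is the management of a coinfected subject's HIV. Section 3.4.4 makes the resistance result the basis for staying on the current regimen. A subject with two values at or above 400 and no rise between them gets no instruction beyond continuing that regimen.

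**Working it through.** The plan states no figure on this point, so there is none to reproduce. The check applies the rule to example pairs, sizes the miss at the confirmation draw, and looks for other routes to a mandated test.

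**1. The rule applied to pairs at least two weeks apart (copies/mL)**

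| First | Repeat | Both at least 400 | Repeat higher | Rebound, plain reading | Rebound with 'and uptrending' deleted |
|---|---|---|---|---|---|
| 410 | 430 | yes | yes | yes | yes |
| 1,000 | 1,000 | yes | no | no | yes |
| 60,000 | 50,000 | yes | no | no | yes |
| 60,000 | 500 | yes | no | no | yes, unless large falls are exempted |

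The third pair differs by log10(60,000/50,000) = 0.08. The fourth falls by log10(60,000/500) = log10(120) = 2.1. The current rule treats the two alike.

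**2. The other reading of the word.** If *uptrending* means up from the suppressed baseline, any two values at or above 400 already satisfy it, and deleting the word changes nothing. Deletion therefore helps on one reading and is harmless on the other.

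**3. Share of pairs missed at the confirmation draw.** The documents give no within-subject variability, no typical viral load at rebound and no trajectory, so every input here is an assumption.

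- Flat true level: the two measured values are exchangeable, and requiring both to be at or above 400 is symmetric in them. So P(repeat not higher) = 1/2, whatever the SD (ignoring ties, which would also fail to trigger).
- True rise of d log10 between draws, per-measurement SD s log10, level well above 400: P(repeat not higher) = Φ(−d / (s√2)).

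| d | s = 0.1 | s = 0.2 | s = 0.3 |
|---|---|---|---|
| 0 | 50% | 50% | 50% |
| 0.1 | 24.0% | 36.2% | 40.7% |
| 0.3 | 1.7% | 14.4% | 24.0% |

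The share is largest for a stable level and shrinks as the true rise becomes large relative to the noise.

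**4. Later chances to meet the definition.** A first value at week 4, 8 or 12 is followed by at least one more scheduled HIV RNA test, so a later, higher value can still bring the mandated test. A first value at post-treatment week 12 is followed only by the two-week confirmation draw; section 5.1 schedules no HIV RNA after that visit.

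**5. The HCV rule beside it.** In section 3.4.2 the repeat has only to meet the same criterion again, for instance HCV RNA at or above LLOQ after 8 weeks. No rise between the first test and its repeat is needed.

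**6. Effect of an exemption for a fall of at least 1 log10.** For a flat true level, P(fall of 1 log10 or more) = Φ(−1 / (s√2)): below 0.0001% at s = 0.1, 0.02% at s = 0.2 and 0.9% at s = 0.3. Almost no flat pairs would be lost, against 50% under the present wording.

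**The case against.** *The word may only be loosely chosen.* Subjects under this rule enter suppressed, below 50 copies/mL or the local LLOQ (section 2.4.1), so staff could take *uptrending* as a rise from suppression. That reading is possible. But the word is joined to *consecutive* and describes the pair of values, so the plain reading is a rise between them. Staff could also apply the two readings differently from subject to subject.

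*A direction test has a purpose.* It avoids labelling a subject who is re-suppressing as a rebound. This stands, and it is why an exemption for large falls is offered. It does not justify excluding level or slightly lower repeats.

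*Other care covers the gap.* Eligibility states that "Subjects must have a primary care doctor for their medical management". Section 2.8 leaves medical problems other than HCV to that provider, and for subjects seen in the community "Copies of results will be sent to the primary care provider". Section 8.4 adds that "Upon recognition of any safety concerns, a teleconference may be held with the MM to discuss the concern". For unexplained abnormal results, section 2.20.1 says "the tests should be repeated immediately and followed up until they have returned to the normal range". All this makes a missed trigger less consequential, most of all at post-treatment week 12, when study drug has been stopped for 12 weeks. None of it mandates a resistance test. An immediate repeat also need not meet the two-week spacing, so it may not complete a qualifying pair.

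*The HCV comparison is imperfect.* Section 3.4.2 decides on stopping study drug, not on genotyping, and one of its four criteria is a rise from nadir. The comparison shows only that confirmation elsewhere in the protocol does not ask the repeat to exceed the first result.

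*A stronger reading to resist.* A reader might infer that half of coinfected subjects with persistent viremia would never be tested. The documents do not support this. The 50% refers to one draw, to pairs already both at or above 400, and to a flat true level. Nor can a chance of never triggering be had by counting the remaining draws. The visit windows in section 2.10 (±7 days at weeks 8 and 12) and the immediate repeats in section 2.20.1 mean that adjacent values need not be two weeks apart.

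**Conclusion.** The point holds as a minor safety-management matter. On the plain reading of section 3.4.4, two values at or above 400 copies/mL without a rise do not trigger the mandated resistance test at the confirmation draw. No other section mandates one.

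The size is about 50% of such pairs if the true level is flat, and less if it is rising. This rests on assumed trajectories and variability. The number of coinfected subjects is not stated, so no count can be given, and it could be zero. For first values during treatment the usual consequence is a later mandated test; post-treatment week 12 is the main gap.

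A reader might also infer that the protocol bars testing in these subjects, or that efficacy conclusions are at risk. Neither follows. The investigator or primary provider may order the test at any time. HIV rebound is not among the listed endpoints, so SVR12, the sample size and the halting rules do not depend on this definition.

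**What to change.** Delete 'and uptrending' from section 3.4.4. Two consecutive post-baseline HIV RNA values of at least 400 copies/mL, two or more weeks apart, then confirm rebound and trigger genotype/phenotype testing on the confirmation sample. Nothing else in the section needs to change. If the sponsor wants to spare subjects who are clearly re-suppressing, add an exemption for a fall of at least 1 log10 between the two draws.

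The cost is two words in an amendment and a few more genotypes on blood already drawn, with no new visit or draw. The downside is that some subjects whose values are falling but still at or above 400 would be classed as rebound and genotyped. The optional exemption removes the steep falls among these, such as 60,000 to 500.
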